8.1.1 Statistical Analysis

All analyses will be performed by QST using SAS® Version 9.3 or later. All summary tables and data listings will be prepared utilizing SAS® software.

The standard operating procedures (SOPs) of QST will be followed in the creation and quality control of all data displays and analyses.

All data listings will be by subject. Additionally, all listings except the screen failure and randomization listings will be by treatment.

8.1.2 Baseline Definition

Baseline is defined as the last non-missing assessment prior to first application of study drug. If the date of first application is unknown due to the subject being lost to follow-up, the Baseline visit record will be used as Baseline if it is non-missing. Missing results will not be flagged as Baseline.

8.1.3 Visit Windowing

Data will be summarized based on nominal visit indications with the exception of data captured at early termination and unscheduled visits. Data from early termination and unscheduled visits will be summarized based on mapped visit values. The analysis windows for early termination and unscheduled visits are presented in the following table.

Analysis Windows for Efficacy and Safety Assessments

Scheduled Visit	Target Study Day	Window (Days)
Week 2	15	8 to 21
Week 4	29	22 to 42
Week 8	57	43 to 70
Week 12	85	71 to 98

Data collected at early termination and unscheduled visits prior to study day 8 will not be analyzed, with the exception of those identified as Baseline values. Data collected at early termination and unscheduled visits after study day 98 will not be included in analyses.

The definition for the study day included in each study window is defined as below:

Study Day prior to Day 1 = Visit Date – Day 1 Date

Study Day on or after Day 1 = Visit Date – Day 1 Date + 1

If an assessment’s mapped visit is a visit at which the subject has data from a scheduled visit present, or if no analyses are planned for the assessment at the mapped visit, the data collected at the early termination or unscheduled visit will not be included in analyses.

In the event of multiple values from unscheduled or early termination assessments within an analysis window, the value closest to the scheduled visit target study day will be used for analyses. If two values tie as closest to the time point (for example, one value is before and the other value is after the time point), then the later value will be selected.

Data collected at all visits will be included in the data listings with visit presented as reported by the site.

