
Primary Efficacy Endpoints:
	
 • Proportion of Patients with an assessment of clear or almost clear and with at least a 2-grade improvement in IGA from baseline at Week 12. • Absolute change from Baseline in lesion count on the face at Week 12 (separately for inflammatory and non-inflammatory lesions).

Secondary Efficacy Endpoints:
	
The secondary efficacy endpoints will be the following:
 
 • Percent change from Baseline, in non-inflammatory lesion count at Week 12. • Percent change from Baseline, in inflammatory lesion count at Week 12. • Proportion of Patients in the E-BPO/E-ATRA cream arm compared to vehicle control achieving at least a 4-point reduction on Item 1 (pimples) of the PRE-FACE from Baseline to Week 12. • Proportion of Patients in the E-BPO/E-ATRA Cream arm compared to vehicle control achieving at least a 4-point reduction on Item 5 (embarrassment) of the PRE-FACE from Baseline to Week 12. • Absolute change from Baseline, in non-inflammatory lesion count at Week 8 • Absolute change from Baseline, in inflammatory lesion count at Week 8. • Absolute change from Baseline, in non-inflammatory lesion count at Week 4. • Absolute change from Baseline, in inflammatory lesion count at Week 4.

Supportive Efficacy Endpoints:
	
 • Proportion of Patients with an assessment of clear or almost clear and with at least a 2-grade improvement from Baseline in IGA, at Weeks 2, 4 and 8. • Absolute change from Baseline in inflammatory and non-inflammatory lesion counts from Baseline to weeks 2, 4 and 8. • PRE-FACE ASD: Mean absolute change in PRE-FACE ASD scores from Baseline to Weeks 2, 4, and 8. • PRE-FACE AID: Mean absolute change in PRE-FACE AID scores from Baseline to Weeks 2, 4, and 8. • Proportion of Patients in treatment relative to control who report at least “minimally improved” as measured by the PGI-C at Week 12. • Patient Global Impress of Symptom Severity (PGI-S) at Week 12. • Patient Global Impression of Treatment Satisfaction (PGI-TS) at Week 12.

Safety Endpoints:
	
 • Adverse events (AEs), including serious adverse events (SAEs) occurring at any time during the trial. • Investigator Cutaneous Safety Assessment and Local Tolerability Assessments score at any time during the trial.

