12.2 Screen Failure and Discontinuation Criteria

A screen failure is a Patient who is not randomized/enrolled in the study due to ineligibility, after signing an ICF, and would not have received study product. The ICF signed by the Patient should be kept with the source document for Patients who do not pass the screening procedures. The documentation should include identification of the eligibility criterion or criteria that were and were not met. The Patient should not be re-screened for this study without Sol-Gel or designee's approval.

Although encouraged to complete the study whenever possible, Patients are free to discontinue their participation in this study at any time and for any reason without prejudice. A Patient may be withdrawn from the study prior to study completion for any of the following reasons:

- Investigator opinion that it is not in the Patient's best interest to continue.
- Patient Request/Withdraw Consent – Whenever the Patient decides it is in his/her best interest to withdraw.
- Lack of Efficacy/Worsening of Condition.
- AE – when the Investigator thinks it's in the Patient's best interest
- Lost to Follow-up – Documentation confirmed at minimum by two phone calls and certified letter. Best efforts should be performed to capture an explanation for the lost-to follow-up event.
- Protocol Violation – When requirements of the protocol are not respected, especially when Patient safety is concerned.
- Pregnancy.

Study staff should make efforts to encourage Patients to complete the study on time. If a Patient prematurely withdraws during the study, every effort should be made to complete at least the Week 12/ End of Study or Early Termination assessments.

In the case of Patients who discontinue due to an AE, the Investigator will conduct follow-up contacts with the Patient until the Investigator, Sponsor and Medical Monitor agree the event is satisfactorily resolved and/or stabilized.

Patients discontinued early from the study shall not be replaced.

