6. STUDY DESIGN

6.1 Overall Study Design

This study will be a randomized, double-blind, multicenter, parallel group, active- and vehicle-controlled pivotal study to assess efficacy, and safety of Products S6G5T-3 and its vehicle for the treatment of acne vulgaris for 12 weeks. Approximately 420 Patients with moderate to severe acne vulgaris (rated 3 or 4 on the 5-point IGA) will be enrolled at up to 31 sites. Patients in this randomized, double-blind, vehicle-controlled, parallel-group multi-center study will be randomly assigned in a 2:1 ratio to Encapsulated Benzoyl Peroxide 3%/Encapsulated All-Trans-Retinoic Acids 0.1% (E-BPO/E-ATRA) Cream or Vehicle Cream respectively. Patients with severe acne vulgaris who are appropriate for systemic treatment need to be counseled regarding their treatment options by the Principal Investigator (PI).

The overall schedule of study visits includes:

- Visit 1/Screening
- Visit 2/Baseline, Day 1

- Visit 3/Week 2, Day 15 (\pm 3 Days)
- Visit 4/Week 4, Day 29 (\pm 3 Days)
- Visit 5/Week 8, Day 57 (\pm 3 Days)
- Visit 6/Week 12, Day 85 (\pm 4 Days) / End of Study or Early Termination

Treatment efficacy will be evaluated using both clinician reported outcome (ClinRO) and Patient-reported outcome (PRO) questionnaires. Clinician reported efficacy assessments will include facial inflammatory and non-inflammatory lesion counts and an IGA which asks assessors to rate Patient's acne from 0 (Clear) to 4 (Severe). Patient reported efficacy assessments include the Patient-Reported Evaluation of Facial Acne (PRE-FACE), the Patient Global Impression of Symptom Severity (PGI-S), the Patient Global Impression of Change (PGI-C), and the Patient Global Impression of Treatments Satisfaction (PGI-TS).

Safety will be assessed at all visits and will include monitoring local and systemic AEs; the Investigator Cutaneous Safety Assessment rating of pigmentation, erythema, dryness and scaling on a scale ranging from 0 (None) to 3 (Severe) and the Patient assessment of Local Tolerability Assessment rating itching, burning and stinging on a scale ranging from 0 (None) to 3 (Severe). A Patient Global Impression of Treatment Side Effects (PGI-SE) will also be administered as part of the study design.

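### The SAP's visit-window rule leaves some early-termination tolerability scores out of the tolerability table, although the protocol's endpoint covers scores at any time

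*SAP*

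**What the plan says.** Protocol 12.2 asks that, when a patient withdraws, "every effort should be made to complete at least the Week 12/ End of Study or Early Termination assessments". The flow chart (Protocol 12.10) and Protocol 12.15 include the cutaneous and local tolerability assessments in that visit.

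SAP 8.1.3 then decides which of these data are analysed. Its window table is headed "Analysis Windows for Efficacy and Safety Assessments", so one rule serves both purposes. Two exclusions matter here:

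- "Data collected at early termination and unscheduled visits prior to study day 8 will not be analyzed", with an exception for values used as Baseline.
- If an assessment's "mapped visit is a visit at which the subject has data from a scheduled visit present", then "the data collected at the early termination or unscheduled visit will not be included in analyses".

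The same sentence also drops an assessment "if no analyses are planned for the assessment at the mapped visit", but tolerability is summarised at all four post-baseline visits, so that clause does not bite here. Values after Day 98 are excluded too. Everything stays in the listings.

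The protocol synopsis gives the safety endpoint as "Investigator Cutaneous Safety Assessment and Local Tolerability Assessments score at any time during the trial". Protocol 7 words it as assessment at Baseline and every study visit. SAP 8.8.1.1 and 8.8.1.2 plan descriptive statistics by treatment group and visit. Table 14.3.1.1 has rows for Baseline and Weeks 2, 4, 8 and 12, and no row for exit or worst scores.

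**The concern.** Within a window, an earlier scheduled score always displaces a later exit score, and any exit in the first week leaves no post-baseline score in the table. For a topical product whose expected reactions are local, the score when a patient stops is among the more informative ones. The sites are asked to collect it, the synopsis endpoint covers it, and the table does not show it.

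At stake is the completeness of the tolerability description. If early exits differ between active and vehicle, the by-visit rows could show an incomplete picture of that difference, with the missing part visible only in patient listings.

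**Working it through.** **Which days are excluded.** The documents state no share of ET data lost, so there is no figure to reproduce. The inputs are the SAP 8.1.3 windows and the scheduled days in SAP 6.1 (for example "Visit 3/Week 2, Day 15"). Assume Weeks 2, 4 and 8 were attended on target. An ET day is excluded if it is before Day 8 or falls after the scheduled visit in the same window.

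| Window | Scheduled day | Excluded ET days | Count |
|---|---|---|---|
| before Day 8 | none | 1–7 | 7 |
| Week 2, Days 8–21 | 15 | 16–21 | 21 − 15 = 6 |
| Week 4, Days 22–42 | 29 | 30–42 | 42 − 29 = 13 |
| Week 8, Days 43–70 | 57 | 58–70 | 70 − 57 = 13 |
| Week 12, Days 71–84 | 85 (not reached) | none | 0 |

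Total: 7 + 6 + 13 + 13 = 39 days.

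**Share, if every exit day is equally likely.**

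- Days 1–84 without the three scheduled days: 84 − 3 = 81, and 39/81 = 48%.
- Counting ET examinations on scheduled days as kept: 39/84 = 46%.
- Starting at Day 2: 38/80 = 47.5%.
- From Day 8 on: 32/74 = 43%.

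**How far this depends on timing.** Simulation, 40,000 exits per scenario, scheduled visits varying by up to 3 days either side:

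| Assumption | Share excluded |
|---|---|
| Even exits | 46% |
| Even exits, 10–30% of visits missed | 42–34% |
| Exits loaded early | 49–54% |
| Exits loaded late | 40% |
| One quarter to one half of ET examinations on a scheduled visit date | 35–23% |
| All on a scheduled visit date | 0% |
| All 1–7 days before the next visit | 6% |
| All 1–14 days after a visit | 77% |

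**In patients.** Number = 420 × dropout × share examined at exit × 39/81. With an assumed dropout of 5–20% (21–84 patients), all examined, this is 10 to 40 patients; with half examined, 5 to 20.

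**What the adverse-event tables recover.** Under Protocol 14.1 and 14.2, the scored reactions are not recorded as adverse events unless they lead to temporary or permanent discontinuation or to a new medication. Two patients show the consequence:

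- One leaves on Day 6 because of burning. It is an adverse event, appears with its severity in the adverse-event tables (SAP 8.8.2, not windowed) and is listed in Listing 16.2.7.2.5. Only the 0–3 score is absent from Table 14.3.1.1.
- One leaves on Day 6 for an unrelated reason with a burning score of 2 and no treatment for it. It is not an adverse event and is in no row of Table 14.3.1.1. The score appears only in Listing 16.2.7.1. The same happens to a Day 40 exit score after a Week 4 visit on Day 29.

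Unscheduled visits behave alike. Protocol 12.16 names discomfort from the study drug as one reason for such a visit, but scoring there is at the investigator's discretion.

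**The case against.** The rule is pre-specified and blind to treatment, and giving scheduled visits priority keeps irregular timings out of the by-visit rows. Protocol 17.5 itself plans these scores at Baseline and Weeks 2, 4, 8 and 12, so the table follows part of the protocol. All of that stands, and it is a reason to leave the by-visit rows alone. It does not meet the synopsis endpoint, which is wider than those visits.

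A reader might go further and infer that the primary efficacy result is biased, because a patient who worsens after Week 4 has Week 12 imputed from the better Week 4 value. The documents do not support that much:

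- An ET value before Day 71 is never a Week 12 value. It could act only through the imputation, and no effect on an estimate or p-value has been shown.
- SAP 8.1.5 resets lesion counts and IGA to Baseline for patients who leave because of a related adverse event or documented lack of effect. The text ties this to the per-protocol population and leaves its use in the intent-to-treat analysis unclear. It does say the reset follows multiple imputation, while the per-protocol analysis otherwise uses last observation carried forward. Where it applies, the exit value is irrelevant.
- The tipping-point analyses (SAP 8.7.2.1.3 and 8.7.2.2.3) already test departures from the imputation assumption.
- Putting a Day 40 value in the Week 4 slot is not the SAP's own preference. Among ET and unscheduled values it takes the one closest to target, and the later one only in an exact tie. Day 40 is 40 − 29 = 11 days off target; Day 29 is on it. The swap would also give a patient two different Week 4 values.

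A reader might also infer that reactions causing withdrawal vanish from safety reporting. They do not: they are recorded as adverse events.

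**Conclusion.** The point holds for the cutaneous and local tolerability scores, as an inexpensive improvement to a descriptive table. SAP 8.1.3 keeps ET and unscheduled assessments out of all tables when they fall before Day 8 or in an occupied window. For these scores that falls short of the protocol's endpoint, and the adverse-event tables fill the gap only in part.

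The size is conditional. Roughly 46–48% of ET assessments before Week 12 are excluded if exits are even and visits on time, and about 23–54% in moderate alternatives. It would be wrong to state that half of all exit data are lost: the documents give no dropout rate or timing, and under the even-dropout assumption slightly more than half are kept. An ET assessment on Days 71–98 counts as Week 12 if no scheduled Week 12 visit exists. A defect in the primary efficacy analysis is not established.

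**What to change.** In SAP 8.1.3, state that the Day 8 cut-off and the occupied-window exclusion do not apply to the cutaneous and local tolerability scores. In Table 14.3.1.1, add either an early-termination/unscheduled row for scores that the by-visit rows leave out, or a worst post-baseline score per patient using all visits. Keep the by-visit rows as they are. If the row is chosen, say which score counts when a patient has several, and whether values after Day 98 belong in it. Under the day count above, scores from 39 of 81 possible exit days would then appear in a table instead of only in listings.

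Leave the primary imputation input unchanged. At most, an optional sensitivity analysis could use the ET value in the imputation.

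The cost is a sentence or two in the SAP, one extra table row and a little programming, with no new data. SAP Section 2 allows updates until the blind is broken. The small downside is a row of irregularly timed values, which is why it should stay apart from the by-visit rows.

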8.1.4 Adjustments for Covariates

Baseline lesion count will be a covariate for the primary efficacy endpoint for acne lesion counts. No other covariates are planned to be used in the analyses for this study.

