11.2 Inclusion Criteria

To be included in the study, Patients must meet the following eligibility /inclusion criteria:

1. Patient must consent to participate, verified by signing an approved written Informed Consent Form (ICF). For Patients under the age of consent, both a signed assent form and a signed ICF from the parent/guardian are required in accordance with local and federal regulations.
2. Male and female 9 years of age and older.
3. Willingness and capacity for protocol compliance (for Patients under the age of consent, the parent/guardian must be willing and able to comply with study requirements).
4. Have a diagnosis of facial acne with ≥ 30 and ≤ 150 non-inflammatory lesions and ≥ 20 and ≤ 100 inflammatory lesions including the nose.
5. Have a score of “3” or “4” (Moderate or Severe) on the IGA scale.
6. Have two (2) or fewer cysts or nodules (defined as an inflammatory lesion greater than or equal to 5 mm in diameter).
7. All females of child-bearing potential and premenarchal, excluding women who are surgically sterile (including Essure procedure, tubal ligation, bilateral oophorectomy or hysterectomy) or post-menopausal: [defined as amenorrhea >12 consecutive months; or women on hormone replacement therapy (HRT) with documented plasma follicle-stimulating hormone (FSH) level >35mLU/mL] for at least 1 year, must use one of the following birth control methods throughout the duration of the study:
 - c) One of these highly effective contraception methods:
 - Intrauterine device (IUD);
 - Hormonal, for at least 3 months. (Pills, injections, implants, transdermal patch, vaginal ring);
 - Abstinence
 - OR
 - d) Double-barrier methods (male and female) of contraception listed below:
 - Combined use of male and female condom;
 - Male condom and female occlusive cap (diaphragm or cervical/vault caps) with spermicidal foam/gel/film/ cream/suppository; or

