12.20 Patient-Reported Outcomes (PRO)

There are five PRO questionnaires to be administered in the study and each is summarized below. Each will be administered to all Patients, from the age of 9 years old, during the designated study visits with instructions from the Study Staff that they be completed:

- Only by the Patient without amendment or interpretation of the Patient's response by a clinician or anyone else.
- Prior to any other assessments or procedures.

In the event the Patient skips any questionnaire item(s); the Study Staff will ask the Patient to complete the form. The PRO questionnaire data will be entered into the eCRF, and a copy will be placed with the Patient source at the site according to the ICH-GCP guideline.

The Patient-Reported Evaluation of Facial Acne (PRE-FACE): The PRE-FACE, which can be completed in less than 2 minutes, is a seven item PRO questionnaire that assesses acne vulgaris-related signs, symptoms and impacts. The four-item acne sign and symptom domain (ASD) assesses the severity of acne vulgaris-related pimples, whiteheads, blackheads, and redness, at their worst, in the 24 hours prior to

administration on an 11-point numeric rating scale (NRS) ranging from 0 (“no [Concept] at all”) to 10 (“[Concept] as bad as you can imagine”). The three-item acne impact domain (AID) assesses acne vulgaris-related embarrassment, self-consciousness, and sadness in the seven days prior to administration on an 11-point NRS ranging from 0 (“not [Concept] at all”) to 10 (“extremely [Concept]”). The PRE-FACE will be administered at study visits 2-6, including Screening, Baseline, and at Weeks 2, 4, 8, and 12/ End of Study or Early Termination.

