8.1.5.3 PRE-FACE Missing Data Imputation

The same procedure will be used for the analyses based on proportion of PRE-FACE item 1 (pimples) and item 5 (embarrassment) successes as the IGA success. Specifically, missing PRE-FACE items 1 and 5 values from which the dichotomized versions are derived will be estimated by MCMC. The pattern of missing observations in each treatment group cannot influence the missing value estimation in the other because the imputation is being conducted independently for each treatment group.

The missing PRE-FACE items 1 and 5 values will be derived for the analysis using the method of MCMC multiple imputation. Multiple imputation and subsequent analysis will involve 3 principal tasks:

1. Create a data set, one for each treatment group, of patients with observed values and those needing estimation by MCMC. The missing PRE-FACE items 1 and 5 values in each data set will be filled in using the MCMC method 5 times to generate 5 data sets. The resulting data sets for each treatment arm will be combined into one complete data set by imputation.

Syntax:

```
proc mi data=datain out=dataout seed=&seed. nimpute=5 <options>;  
  where trtpn=(1, or 2);  
  mcmc chain=multiple;  
  var baseline week2 week4 week8 week12;  
run;
```

2. For each complete data set, the dichotomous success rate (at least a 4-point reduction from Baseline) will be computed. The estimated global values will be rounded to the nearest integer value prior to evaluating the success rate. Each complete data set will be analyzed with a logistic regression with factors of treatment group and analysis center.
3. The results from these analyses will be combined into a single inference using SAS PROC MIANALYZE.

The following 4 random seeds have been pre-specified by using a random number generator:

- PRE-FACE Pimples Scores; S6G5T-3: Seed = 1597410322
- PRE-FACE Pimples Scores; S6G5T-3 Vehicle: Seed = 466920922

- PRE-FACE Embarrassment Scores; S6G5T-3: Seed = 288784276
- PRE-FACE Embarrassment Scores; S6G5T-3 Vehicle: Seed = 1746263137

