8.1.8 Multiple Comparisons/Multiplicity

The overall Type I error will be controlled by requiring the three co-primary efficacy endpoints to be statistically significant. Specifically, failure of either one of the primary efficacy endpoints will invalidate the statistical significance of the secondary efficacy endpoints.

Evaluation of the secondary efficacy variables will use a gated sequential procedure starting with the comparisons of the first step and proceeding onto the next step and etc.

A stepwise process will be conducted for testing the secondary efficacy endpoints in order to control for multiplicity. These tests will be performed for only the ITT population. The testing process will terminate whenever a statistical test for a step is not significant. All subsequent tests for the remaining steps will be considered not significant. The order of testing is provided below.

Step Number	Secondary Endpoint
1	Percent change from Baseline, in non-inflammatory lesion count at Week 12.
2	Percent change from Baseline, in inflammatory lesion count at Week 12.
3	Proportion of patients in the E-BPO/E-ATRA cream arm compared to vehicle control achieving at least a 4-point reduction on Item 1 (pimples) of the PREFACE from Baseline to Week 12.
4	Proportion of patients in the E-BPO/E-ATRA Cream arm compared to vehicle control achieving at least a 4-point reduction on Item 5 (embarrassment) of the PRE-FACE from Baseline to Week 12.
5	Absolute change from Baseline, in non-inflammatory lesion count at Week 8
6	Absolute change from Baseline, in inflammatory lesion count at Week 8.
7	Absolute change from Baseline, in non-inflammatory lesion count at Week 4..

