8.7.3 Secondary Efficacy Analysis

Appropriate descriptive statistics will be computed for all secondary efficacy parameters.

Additionally, all inferential testing of percent change in lesions will follow the methods for the primary lesion count analyses. Methods corresponding to the analysis of IGA will be used to compare the proportion of patients in the E-BPO/EATRA Cream arm versus vehicle control achieving at least a 4-point reduction in pimples (item1 of the PRE-FACE) or in embarrassment (item5 of the PRE-FACE) scores from Baseline to Week 12.

A stepwise process will be conducted for testing the secondary efficacy endpoints in order to control for multiplicity, refer to Section 8.1.8.

The secondary efficacy analysis will be presented on the ITT and PP populations.

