LSSD ^a	xx.xx	xx.xx		x.xxx ^c
Non-Inflammatory Lesion Count – Percent Change from Baseline to Week 12				
LSMean ^a	xx.x	xx.x	x.xxx ^b	x.xxx ^a
LSSD ^a	xx.xx	xx.xx		x.xxx ^c
At Least 4-Point Reduction on Item 1 (Pimples) of the PRE-FACE from Baseline to Week 12				
Success	xx.x%	xx.x%	N/A	x.xxx ^d
Failure	xx.x%	xx.x%		
At Least 4-Point Reduction on Item 5 (Embarrassment) of the PRE-FACE from Baseline to Week 12				
Success	xx.x%	xx.x%	N/A	x.xxx ^d
Failure	xx.x%	xx.x%		

^a Least squares means, standard deviations and treatment p-value from an analysis of covariance with factors of treatment and analysis center and the respective Baseline lesion count as a covariate. Negative least squares means values represent decrease from Baseline.

^b Skewness test, based on methods presented by J.H. Zar (1984), assessed for each imputed dataset. The average p-value is presented.

^c P-value from a ranked analysis of covariance with factors of treatment and analysis center and the respective Baseline lesion count as a covariate.

^d P-value from a logistic regression with factors of treatment group and analysis center.

Note: Multiple imputation (MCMC) used to impute missing values.

SOURCE: USERNAME\SPONSOR\PROJECT\JOBNAME (DATE, TIME)

{NOTE TO PROGRAMMER: ADJUST FOOTNOTE “d” IF FIRTH’S PENALIZED LIKELIHOOD IS NEEDED}

Table 14.2.8.1: Secondary Efficacy Analyses
(Intent-to-Treat Population)
(Page 2 of 3)

	E-BPO/E-ATRA 3%/0.1% Cream (N=xxx)	Vehicle Cream (N=xxx)	Skewness P-Value	Treatment P-Value
Inflammatory Lesion Count –Absolute Change from Baseline to Week 8				
LSMean ^a	xx.x	xx.x	x.xxx ^b	x.xxx ^a
LSSD ^a	xx.xx	xx.xx		x.xxx ^c
Non-Inflammatory Lesion Count –Absolute Change from Baseline to Week 8				
LSMean ^a	xx.x	xx.x	x.xxx ^b	x.xxx ^a
LSSD ^a	xx.xx	xx.xx		x.xxx ^c

^a Least squares means, standard deviations and treatment p-value from an analysis of covariance with factors of treatment and analysis center and the respective Baseline lesion count as a covariate. Negative least squares means values represent decrease from Baseline.

^b Skewness test, based on methods presented by J.H. Zar (1984), assessed for each imputed dataset. The average p-value is presented.

^c P-value from a ranked analysis of covariance with factors of treatment and analysis center and the respective Baseline lesion count as a covariate.

^d P-value from a logistic regression with factors of treatment group and analysis center.

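### The PRE-FACE responder tests at gated steps 3 and 4 omit the baseline item score (valid but less efficient), and the supportive PRE-FACE shells name a lesion-count covariate and test no ASD or AID score

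*SAP*

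**What the plan says.** **Responder tests.** A PRE-FACE item response is a fall of at least 4 points from Baseline to Week 12. Items 1 and 5 are scored on "an 11-point numeric rating scale (NRS) ranging from 0" to 10 (protocol 12.20). For the analysis, SAP 8.1.5.3 step 2 says "Each complete data set will be analyzed with a logistic regression with factors of treatment group and analysis center". SAP 8.7.3 and protocol 17.4.3 take the same route: "Methods corresponding to the analysis of IGA will be used to compare the proportion of patients". Footnote d of the shell for Table 14.2.8.1 repeats the model: "P-value from a logistic regression with factors of treatment group and analysis center". SAP 8.1.4 closes the list of covariates: "No other covariates are planned to be used in the analyses for this study". The baseline item score appears in the imputation syntax of 8.1.5.3 but not in the final regression.

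**Place in the sequence.** Items 1 and 5 are steps 3 and 4 in SAP 8.1.8, where "The testing process will terminate whenever a statistical test for a step is not significant". The Week 8 and Week 4 lesion endpoints come after them.

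**Supportive PRE-FACE endpoints.** SAP 7.1.3 and protocol 17.3.3 name the mean change in ASD and AID scores at Weeks 2, 4 and 8. SAP 8.7.4 has continuous supportive variables follow the lesion-count method. Tables 14.2.12.1 and 14.2.13.1 are titled for ASD and AID scores, but their rows are items 1-4 and items 5-7. Their footnotes a and c adjust for the baseline lesion count said to belong to each variable.

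**The concern.** There are three separate issues.

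1. **Efficiency at steps 3 and 4.** The baseline score sets who can respond: from 0, 1, 2 or 3, a 4-point fall is impossible. Entry criteria fix an IGA grade and lesion counts ("≥ 20 and ≤ 100 inflammatory lesions including the nose" for inflammatory lesions), but no minimum item score. A strong predictor that is already collected is left out of two tests that act as gates. A miss at either step ends testing of every later lesion endpoint.

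2. **Wrong covariate and missing test in the supportive shells.** Redness, embarrassment, self-consciousness and sadness have no lesion count of their own, and the trial has two lesion counts to choose from. Programmed as written, the model would use an unrelated or undefined covariate. The ASD and AID scores that define the endpoint would have no p-value anywhere.

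3. **Wording.** SAP 8.1.4 limits the lesion-count covariate to the primary endpoint, yet the shells for the secondary and Week 2 lesion endpoints also use it.

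**Working it through.** **No plan figure to reproduce.** Neither document gives a response rate, baseline distribution, correlation or power for any PRE-FACE item. All magnitudes below rest on assumed inputs. From the documents come only 280 vs 140 patients, two-sided 0.05, the 0-10 scale and the 4-point cut.

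**Simulation model.**
- Baseline b = round(N(mu, sd)), limited to 0-10.
- Week 12 = round(mu - drop - effect x active + rho x (b - mu) + N(0, sd^2(1 - rho^2))), limited to 0-10.
- Response: b minus Week 12 is 4 or more.
- Logistic Wald test of treatment at 1.96, fitted to the same data with and without b as a linear term; 3,000 trials per scenario; missing data not simulated.
- Grid: 5 (mu, sd) pairs x 4 values of rho (0.3, 0.5, 0.7, 0.9) x 2 drops (1.2, 2.0) x 6 effects (0.5, 0.7, 0.9, 1.1, 1.3, 1.6) = 240 scenarios.

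The share below 4 at baseline is Phi((3.5 - mu)/sd); for example (3.5 - 6)/2.5 = -1, which gives 15.9%.

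| mu, sd | Share below 4 | Median gain (points) | Maximum gain (points) |
|---|---|---|---|
| 8, 1.8 | 0.6% | 0.2 | 8.0 |
| 7, 2.2 | 5.6% | 1.0 | 10.0 |
| 6, 2.5 | 15.9% | 3.0 | 11.5 |
| 5, 2.5 | 27.4% | 5.1 | 16.3 |
| 4.5, 2.8 | 36.0% | 7.2 | 19.3 |

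**Results over the grid.**
- All 240: median 2.7 points, quartiles 0.2 and 6.8. Gain under 1 point in 90, 5 or more in 88, hence 1 to 5 in the other 240 - 90 - 88 = 62.
- 228 scenarios lie between about 0 and 14. The other 12 (up to 19.3) all need at least 27% of patients below 4 and rho of 0.5 or less; they are not relied on. Seven scenarios are slightly negative (lowest -0.27), which is no gain.
- By rho 0.3, 0.5, 0.7, 0.9: medians 7.3, 5.2, 1.5, 0.0.
- Unadjusted power 95% or more (79 scenarios): -0.1 to +2.9, median 0.1. Power 50-90% (78 scenarios): median 6.6.
- Share below 4 of 16% or less (144 scenarios): -0.3 to +11.5, median 1.0.
- No effect, 20,000 trials each: with response rate 5% or more (33 scenarios), rejection 4.2-5.2% unadjusted and 4.2-5.5% adjusted; with lower rates (7 scenarios), at most 3.4% for both.

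**With analysis center in the model** (20 centers of 21 patients, center SD 0.5, rho 0.5, drop 1.2, 1,500 trials):
- Effect 0.9: power 88.3 to 90.9, 78.2 to 82.3, 67.1 to 74.3, 60.8 to 70.3 and 44.7 to 56.2% for the five rows above, i.e. gains of 2.6, 4.1, 7.2, 9.5 and 11.5 points.
- Effect 1.6: gains 0.0, 0.1, 0.1, 1.9 and 4.6 points.
- No effect: 5.0-5.9% unadjusted, 5.2-6.1% adjusted (simulation SE about 0.6 point).

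**Second simulation with other inputs** (14 centers; mean 5, 6 or 7; SD 2.3; correlation 0.3 or 0.5; vehicle change -1.8; shift 0.6 or 0.8; 1,500 trials). Power rose in all 12 scenarios. Smallest gain: 47.2 to 51.3%, 4.1 points. Largest: 47.7 to 61.1%, 13.4 points. Unadjusted power was 29.5-71.3%, so these are moderate-power cases. Rejection under no effect was 3.7-5.9% without and 4.4-6.7% with the baseline score (SE about 0.6 point).

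**Shells against endpoint.** The stated endpoints give 2 domains x 3 visits = 6 comparisons. The shells give 7 items x 3 visits = 21, none of them a domain score. No other planned table tests ASD or AID, and SAP section 10 logs no change. The available text has no rule for combining the items (Appendices 2 and 3 are not shown), whereas SAP 8.7.5 scores Acne-QoL in full, including missing items. The shells impute only items 1 and 5, so a domain score would mix imputed and unimputed items.

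**The case against.** **The planned responder model is valid and consistent across both documents, so this is preference.** The first half is true and is why no contradiction is claimed. What remains is whether a low-cost gain at a gate is worth taking.

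**The gain may be nil.** The only responder gap in the documents is for IGA, 33.3% - 12.6% = 20.7 points. Where the simulated PRE-FACE gap is 19-23 points (23 scenarios), the gain is 0.0 to 2.9, median 0.2. Entry at IGA 3-4 with at least 20 inflammatory lesions also makes low item 1 scores less likely. Both points stand. The grid is a set of assumptions, not a forecast, and imputation was not simulated.

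**IGA baseline also limits response** (a 2-grade fall from 3, a 3-grade fall from 4), yet no change is asked there. The parallel is fair but weaker: both IGA entry grades can respond, whereas PRE-FACE 0-3 cannot.

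**A linear term is misspecified where response is impossible.** Also true. But the simulated data contain those impossible responders. With the linear term, rejection under no effect was close to that of the unadjusted test; the slightly higher upper values are within or near simulation error.

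**ASD scores may mean the set of items.** This reading is possible, since protocol 12.20 describes item groupings and no composite. It does not rescue the lesion-count footnote, and the SAP should say which reading applies.

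**Conclusion.** The concern holds. The responder tests at steps 3 and 4 are valid but can lose power. The loss is about 0 to 14 points in 228 of 240 assumed scenarios, median 2.7 overall. It is negligible if the effect is large or baseline and Week 12 are highly correlated, and material if power is moderate and many patients start below 4. The true size cannot be derived from the documents.

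The lesion-count covariate in Tables 14.2.12.1 and 14.2.13.1 is an error. The absence of an ASD or AID test is a mismatch with SAP 7.1.3 unless item-level change was intended. These endpoints lie outside the gated sequence, so type I error control is not affected. The changes should be made; they are not a condition for a valid trial. Confidence is medium because the power figures rest on assumed inputs.

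**What to change.** Before unblinding:

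1. In SAP 8.1.5.3 step 2 and 8.7.3, add the baseline score of the same item, as a linear term, to the item 1 and item 5 responder models. Give the PRE-FACE rows of Tables 14.2.8.1 and 14.2.8.2 a matching footnote. Log the departure from protocol 17.4.3 in SAP section 10. Keep the response percentages by arm.
2. In footnotes a and c of Tables 14.2.12.1 and 14.2.13.1, replace the lesion count by the baseline value of the PRE-FACE variable analysed. Then either define ASD and AID scoring, including missing items, and add rows that test the scores, or restate the endpoint in 7.1.3 as item-level change.
3. Reword 8.1.4 to match the models: own baseline lesion count for all lesion endpoints; baseline PRE-FACE value for PRE-FACE responder and change analyses; no covariate, and no change, for IGA, PGI-C, PGI-S and PGI-TS.

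Cost: SAP text, shell footnotes, one model term, and a scoring rule with added rows if domain scores are kept. No new data or patients. The PRE-FACE odds ratio becomes conditional on baseline rather than marginal.
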